9.1.2 Treatment Replacement

In the event that a subject's original container is lost, damaged, or consumed prior to the end of treatment, the Investigator will use the ORS, which will specify a new Kit Number to be dispensed to that subject from the supplies already available at the site.

9.2 Masking

The study subject, investigational staff, investigator, and sponsor personnel will be masked with respect to treatment group. The investigational site will employ procedures to avoid accidental unmasking of the masked staff. A sealed copy of the randomization scheme will be retained at the investigational site and will be available at the time of the site inspection to allow for verification of the treatment identity of each subject.

Masking codes should be broken only in emergency situations for reasons of subject safety. Whenever possible, the investigator or sub-investigator will consult with a member of the study team prior to breaking the mask. When the masking code is broken, the reason must be fully documented. At the initiation of the study, the study site will be instructed on the method for breaking the masking. The method will either be a manual or an electronic process.

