To account for 10% attrition, approximately 624 subjects will be randomized in order to ensure that 560 subjects complete the 42 days (6 weeks) of dosing. Subjects who meet all inclusion/exclusion criteria will be randomized to receive the generic brinzolamide 1% suspension or brinzolamide 1% suspension (AZOPT®) using computer generated, blocked treatment assignments in a 1:1 ratio stratified by investigational site. Investigational product will be administered at approximately 8:00 AM, 4:00 PM and 10:00 PM in both eyes for 42 days, with exception of Visit 1 (Day 1) dose administered at only 4:00PM and 10:00PM. IOP assessments will be performed at approximately 8:00 AM and 10:00 AM on days 1 (baseline), 14, 21, and 42. IOP will be performed a second time (at approximately 10:00AM) on Days 1 (baseline), 14, 21, and 42. For subjects who discontinue the study before the end

of the treatment period, an Early Termination visit will be conducted within approximately one week after last study dose.

Figure 1 Study Design

[figure not shown]

Table 2 Study Design and Schedule of Assessments

Visit identifier	Screening	Visit 1	Visit 2	Visit 3	Visit 4	Early Termination
Visit Window	Day -42 to -4	Day 1	Day 14 ±4 days	Day 21 ±4 days	Day 42 ±4 days	Approximately within 7 days after last dose
Informed Consent	X					
Obtain Subject ID	X					
Randomization		X				
Inclusion/Exclusion criteria	X	X				
Demographics	X					
Medical History	X					
Prior and Concomitant medications	X	X	X	X	X	X
AE Monitoring	X	X	X	X	X	X
Check dosing diary			X	X	X	X
Collect unused investigational product				X	X	X
Collect dosing diary				X	X	X
BP and Pulse (sitting)	X	X	X	X	X	X
Visual Field Testing	X ^C					
Refraction	X	X*	X*	X*	X*	X*
BCVA	X	X	X	X	X	X
Biomicroscopy	X	X	X	X	X	X
Intraocular Pressure	X	X ^B	X ^B	X ^B	X ^B	X
Gonioscopy	X ^D					
Pachymetry	X					
Ophthalmoscopy	X	X	X	X	X	X
Urine Pregnancy Test	X	X			X	X
Dispense Investigational Product		X		X		
Dispense Dosing Diary		X		X		
Self-Administer Investigational Drug ^A			X ^A	X ^A	X ^A	

^A: indicates dosing will be self-administered at the site on visits 2, visit 3, and visit 4 after 8:00AM IOP measurement
^B: IOP measurement will occur twice (within ± 30 minutes of) 8:00AM and 10:00AM) at visit 1, visit 2, visit 3, and visit 4
^C: Visual Field testing to be conducted if no documentation within 6 months prior to screening
^D: Gonioscopy testing to be conducted if no documentation within 6 months prior to screening

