10.1 Brinzolamide 1% Suspension

10.1.1 Packaging and Labeling

The generic brinzolamide 1% suspension and brinzolamide 1% suspension (AZOPT®) will be provided by the Sponsor as 10 mL topical ophthalmic solutions. Each mL of the generic brinzolamide 1% suspension and Brinzolamide 1% suspension (AZOPT®) contains 10 mg of brinzolamide (1% w/v) and one drop of each medication (approximately 0.03 ml) contains approximately 0.3 mg of brinzolamide. The generic brinzolamide 1% suspension and brinzolamide 1% suspension (AZOPT®) will be supplied in eyedropper bottles that are in masked external packaging. Investigational product will be dispensed on Day 1 and on Day 21. Investigational product will be labeled according to local regulatory requirements with appropriate dosing and storage information as well as a unique container number that will be used to assign the medication to the subject according to their treatment assignment. Investigational product will be supplied in sufficient quantities to allow unopened containers to be kept as bioequivalence retains. Bioequivalence retains should be stored in accordance with protocol-specified requirements for at least 5 years following the date on which the application or supplemental application is approved, or, if such application or supplemental application is not approved, at least 5 years following the date of completion of a bioavailability or bioequivalence study. The quantity and storage of bioequivalence retains will be outlined in separate instructions to the site.

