10.1.3 Study Drug Preparation and Dispensing

Investigational product should not be used more than 28 days after opening. It will be dispensed using ORS on Day 1 and Day 21 to ensure the subject has a sufficient amount of investigational product for the duration of treatment. A qualified and experienced member of the investigational site staff will dispense the investigational product in masked external packaging provided throughout the course of dosing. Investigational site staff must not be in

the room whenever the treatment is taken out of the masked external packaging. The bottle that is dispensed on Day 1 will be returned to the site in the masked external packaging on Day 21 (Visit 3), at which time a second bottle (again, in masked external packaging) will be dispensed to the subject; unused investigational product that was dispensed on Day 21 must be returned in the masked external packaging at the end of the Day 42 (Visit 4) (eg, after all assessments are performed). Note: The subject should also bring their bottle to Visit 2 for purposes of the in-office dose.

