10.1.4 Administration

Administration instructions should be followed, which are on the investigational product label.

Each dose of investigational product (one eye drop) will contain 0.3 mg brinzolamide in either the generic brinzolamide 1% suspension or brinzolamide 1% suspension (AZOPT®).

One drop of investigational product should be instilled in each eye at approximately 8:00 AM, 4:00PM, and 10:00PM daily. On Day 1, the first day of dosing, only the 4pm and 10:00PM should be administered. On Day 42, the last day of dosing, only the 8:00AM dose is administered.

Subjects will self-administer investigational product daily on an outpatient basis; however, on Day 14, Day 21, and Day 42 the 8:00AM dose will be self-administered at the investigational site, following the 8:00AM IOP. The dose must be self-administered in a secluded room without any investigational site staff present within 30 minutes of 8:00 AM. Investigational site staff must not be in the room whenever the treatment is taken out of the masked external packaging or the subject is dosed with investigational product.

Subject knowledge and understanding of the dosing requirements must be verified before the subject leaves the investigator site at each visit.

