10.2 Study Drug Accountability

The investigative site must maintain adequate records documenting the receipt, use, loss, or other disposition of the investigational product supplies. Unused investigational product that was dispensed on Day 1 must be returned in the masked external packaging to the

investigator at the Day 21 visit at which time another bottle (again, in masked external packaging) will be dispensed to the subject; unused investigational product that was dispensed on Day 21 must be returned in the masked external packaging at the end of the Day 42 visit (eg, after all assessments are performed and 8:00AM dose is instilled). The investigational site will employ procedures to avoid accidental unmasking of the masked staff. Investigational product accountability will be discussed in the study monitoring plan.

At various time points throughout the study and/or upon completion of the study, Valeant or representative of Valeant will review and verify the Investigator's accountability records. Following verification, and as directed by Valeant, all used and unused product must be returned to Valeant at the addresses below, or with Valeant's permission, disposed of at the site in an appropriate manner.

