11.1.2 Visit 1 (Day 1)

Subjects must continue to satisfy all inclusion/exclusion criteria in order to be eligible for randomization.

The following procedures will be completed:

- Re-check inclusion/exclusion criteria (only those eligibility criteria that apply at Day 1);
- Review prior/concomitant treatments;
- Blood pressure/pulse rate (sitting);
- Best corrected visual acuity;

NOTE: Refraction must be performed if a decrease in VA of two or more lines from the previous assessment occurs.

- Biomicroscopy
- IOP at 8:00 AM \pm 30 minutes and 10:00 AM \pm 30 minutes;
- Ophthalmoscopy
- Assess and record adverse events (AEs);
- Urine hCG for all females of childbearing potential;
- Randomize the subject to a treatment group;

- To prepare for study participation, subjects will be instructed on the use of Concomitant Medications ([Section 9.3](#));
- Dispense dosing diary and instruct subject on completion;
- Dispense investigational product in masked external packaging and instruct subject on self-administration, storage, and return.
- First dose will be self-administered at 4pm, then followed by 10pm dose.

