11.1.4 Visit 3 (Day 21)

The following procedures will be completed on Day 21 \pm 4 days:

- Review concomitant treatments;
- Collect dosing diary, and dispense new dosing diary;
- Blood pressure/pulse rate (sitting for 5 minutes);
- Best corrected visual acuity;

NOTE: Refraction must be performed if a decrease in VA of two or more lines from the previous assessment occurs.

- Biomicroscopy;
- IOP at \pm 30 minutes 8:00 AM (prior to 8:00 AM dose of investigational product) and 10:00 AM. The 8:00 AM dose must be self-administered within 30 minutes of 8:00 AM in a secluded room without any investigational site staff present. Investigational site staff must not be in the room whenever the treatment is taken out of the masked external packaging or the subject is dosed with investigational product. Subject knowledge and understanding of the dosing requirements must be verified before the subject leaves the investigator site at each visit;
- Ophthalmoscopy
- Assess and record AEs;
- Collect the unused investigational product in the first bottle;
- Dispense investigational product in masked external packaging and instruct subject on the self-administration, storage, and return of product at visit 4.

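### Is the mask broken because subjects are not told to keep quiet about the bottle they unpack?

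*Combined protocol and SAP*

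**What the plan says.** - **Who is masked.** Section 9.2: "The study subject, investigational staff, investigator, and sponsor personnel will be masked with respect to treatment group".
- **What is masked.** Section 10.1.1 says that both products "will be supplied in eyedropper bottles that are in masked external packaging". It gives both arms the same 10 mL format and a study label with dosing and storage information and a container number. It does not say whether the inner bottles and labels are identical or over-labelled.
- **Staff and the unpacked bottle.** Section 10.1.4: "Investigational site staff must not be in the room whenever the treatment is taken out of the masked external packaging". Section 10.1.3 has the same rule, and sections 11.1.3 to 11.1.5 repeat it for each on-site dose, taken in a private room.
- **When the bottle is at the site.** Footnote A of Table 2 (section 7.1) "indicates dosing will be self-administered at the site on visits 2, visit 3, and visit 4 after 8:00AM IOP measurement". Section 10.1.3 adds for Day 14: "The subject should also bring their bottle to Visit 2 for purposes of the in-office dose".
- **What subjects are told at dispensing.** Visit 1 (section 11.1.2): "Dispense investigational product in masked external packaging and instruct subject on self-administration, storage, and return". Visit 3 (section 11.1.4): "Dispense investigational product in masked external packaging and instruct subject on the self-administration, storage, and return of product at visit 4".
- **What sites must do.** Section 10.2, as in section 9.2: "The investigational site will employ procedures to avoid accidental unmasking of the masked staff".

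**The concern.** The rule sending staff out of the room treats the bottle as something that might reveal the arm. The subject handles that bottle at every dose, and on Days 14, 21 and 42 does so on site between the two IOP readings. The rules govern what staff see, and nothing in the protocol governs what the subject says. Brinzolamide users may enrol after washout (Table 1), so someone who knows the marketed bottle could recognise it if it were not disguised.

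The outcomes are not immune to an unmasked assessor. IOP is a manual Goldmann reading in which the operator turns a dial (section 11.8), and causality of adverse events is the investigator's judgement (section 12.3). The equivalence limits are narrow: 95% confidence intervals within ±1.0 mmHg at three of four time points and within ±1.5 mmHg at all four (section 13.2.1). If knowledge of the arm leaked to the reader, an artificial difference could make equivalent products fail, and an unconscious pull towards equality could help different products pass.

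**Working it through.** The question is whether the plan as written leaves an open route from bottle to assessor. No figure in the plan bears on that directly, so steps 1 to 4 set the sections side by side. Steps 5 and 6 show what numbers can and cannot add.

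1. **Route by sight.** Staff may not be present when the bottle leaves its pack (10.1.3, 10.1.4, 11.1.3 to 11.1.5). Used product comes back in the masked pack (9.4, 10.1.3, 10.2). Staff could see an unpacked bottle only if these rules were broken. This route is closed.

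2. **Route by speech.** The instructions to subjects cover dosing, storage, return, the diary, missed doses and other medication (9.3, 9.4, 10.1.4, 11.1.2, 11.1.4). None asks for silence about the bottle. In the protocol text this route is covered only by the general site duty in 9.2 and 10.2.

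3. **What a remark would need to reveal.** The design is parallel-group, so each subject handles one product and has nothing to compare it with. A remark identifies the arm only if the bottle carries a brand or a shape that someone knows. Section 10.1.1 describes both arms alike. The dispenser in section 16 of the appended label is how the marketed product is sold and says nothing about trial supply. The staff rule fits recognisable bottles, but it also fits simple precaution.

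4. **Where an instruction could sit.** The protocol points to site procedures against unmasking (9.2, 10.2), the study label for administration (10.1.4), a product manual (10.1.2) and the dosing diary (11.1.2). There is also the consent form. None of these was reviewed, so their silence cannot be assumed.

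5. **Counts of handling do not measure the risk.** With 2 doses on Day 1 and 3 a day afterwards, doses before hour 0 of Day D number 2 + 3 × (D − 2). That is 38 for Day 14 and 122 for Day 42. Home handling therefore precedes all four primary readings, and singling out the two hour-2 readings that follow an on-site dose separates nothing. These are scheduled doses, not unmasking events.

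6. **How large a bias would matter (a what-if, not an estimate).** Section 13.1 gives SD 3.3 mmHg, 280 evaluable subjects per group, correlation 0.565 and a true difference of 0.
   - Standard error = 3.3 × √(2/280) = 0.279. Half-width of the 95% interval = 1.964 × 0.279 = 0.548.
   - Simulating the two-part rule, with the SD taken as known, gives 90.6% power. This reproduces the stated 90%.
   - The table adds a constant arm-average bias at all four time points. The last column assumes a true difference of 1.0 mmHg that the bias shrinks.

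| Bias (mmHg) | Pass if true difference is 0 | Pass if true difference is 1.0, shrunk by the bias |
|---|---|---|
| 0 | 90.6% | 0.5% |
| 0.1 | 87.6% | 1.7% |
| 0.2 | 79.1% | 4.4% |
| 0.3 | 65.7% | 10.0% |
| 0.5 | 33.2% | 33.2% |

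   - These are averages over a whole arm. Suppose, as an assumption, that the reader is unmasked for a fraction f of one arm only. An average bias of 0.1 mmHg then needs an error of 0.1/f in each affected reading: 2 mmHg at f = 5%, 1 mmHg at f = 10%, and 0.2 mmHg at f = 50%. The documents support no value of f, including any value above zero.

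**The case for a change.** The best case for a change is that a remark is foreseeable and a sentence is cheap. The protocol requires conversation about the drug: missed doses are discussed with site personnel (9.4), understanding of dosing is checked at each visit (10.1.4), medication is reviewed at each visit (9.3), and a lost or damaged container goes through the investigator (9.1.2). The duty to avoid accidental unmasking is general and addressed to sites, so practice could vary across approximately 32 of them. The rule for two or three readings in section 11.8 limits the reader's discretion but does not remove it.

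The factual part stands. The protocol contains no such instruction and does not say whether the inner bottles match. The consequence does not follow. A foreseeable remark is harmless unless the bottle is recognisable, and nothing shows that it is. If the bottles match, the instruction protects nothing. A blanket ban on describing the bottle or its label would also get in the way of reporting a damaged container under section 9.1.2 unless it carried an exception. Varying practice between sites is a matter for site training and monitoring, which sections 14.1 and 10.2 provide for.

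**Conclusion.** No change is needed. The visual route is closed by explicit rules. The spoken route is covered by a general site duty and matters only if the two bottles can be told apart, which the documents leave unstated. Following the plan as written is not shown to give a wrong or worse result for IOP or for adverse events. The size and direction of any bias cannot be derived. The figures in the working show only that the equivalence rule is sensitive to an arm-wide bias of a few tenths of a mmHg, not that one is likely.

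This rests on two assumptions: that sites carry out the duty in sections 9.2 and 10.2, and that trial bottles are labelled as section 10.1.1 describes, without recognisable branding. Evidence that the reference product was dispensed in its commercial bottle with the brand visible would reopen the question.

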9.3 Concomitant Medications

Subjects must abstain from the concomitant medications prohibited in the Exclusion Criteria ([Section 8.2](#)) of this protocol.

All medications taken during the study must be recorded with indication, daily dose, and start and stop dates of administration. All subjects will be questioned about concomitant medications at each clinic visit.

Subjects who anticipate the need to initiate or modify medication (systemic or topical) that is known to affect IOP or blood pressure (BP) (eg, β -adrenergic antagonists, α -adrenergic agonists, calcium channel blockers, angiotensin-converting enzyme (ACE) inhibitors, and angiotensin II receptor blockers) during the study period should not be enrolled.

The following prescription and over-the-counter drug products, procedures, and activities are prohibited during the study:

- Ocular hypotensive drug product other than study treatment, eg, acetazolamide (Diamox®), betaxolol (Betoptic®, Betopic-S®), betaxolol and pilocarpine (Betoptic® Pilo), bimatoprost (Lumigan®), brimonidine tartrate (Alphagan®, Alphagan® P), brimonidine tartrate and brinzolamide (Simbrinza®), brimodidine tartrate and timolol maleate (Combigan®), carbachol (Miostat®), carteolol (Ocupress®), dorzolamide hydrochloride (Trusopt®), dorzolamide hydrochloride and timolol maleate (Cosopt®), epinephrine (Epifrin®), latanoprost (Xalatan®), levobetaxolol (Betaxon®), levobunolol (Akbeta®, Betagan®), mannitol (Osmitrol®), metipranolol (OptiPranolol®), pilocarpine (Isopto® Carpine, Pilopine HS®), tafluprost (Zioptan™), timolol (Betimol®, Istalol®, Timoptic®, Timoptic XE®), travoprost (Travatan®, Travatan Z®);
- Ophthalmic over-the-counter or prescription product, other than study treatment and the occasional use of artificial tears;
- Oral carbonic anhydrase inhibitor;
- High-dose salicylate therapy; defined as stable daily doses exceeding 325 mg aspirin or equivalent
- Topical Corticosteroid
- Systemic corticosteroid;
- Topical ophthalmic corticosteroid;
- Intraocular corticosteroid implant;
- Intravitreal or subtenon injection of ophthalmic corticosteroid;

- Marijuana (any form)
- Change in concurrent treatment or initiation of treatment with agents potentially affecting IOP, eg, antihypertensive medication;
- Ocular surgery during the study.

Administration of all medications used up to 30 days prior to study entry (date ICF signed) through study exit must be recorded in the source documentation and in the Concomitant Medications eCRF. Indications for these medications should be recorded in the subject's Medical History eCRF, as applicable.

9.4 Treatment Compliance

Subjects should be instructed that if they miss a dose, this should be recorded in their dosing diary and discussed with the investigational site personnel at the next contact or visit.

Subject's knowledge and understanding of the dosing diary completion must be verified before the subject leaves the investigator site at each visit.

Compliance of outpatient dosing will be assessed by site personnel at Day 14, Day 21, and Day 42 by review of the subject's dosing diary.

The dosing diary along with the investigational product, in its masked external packaging, will be collected from the subject at Visit 3 and also at the end of the subject's participation in the study.

9.5 Protocol Deviations

A deviation from the protocol is an unintended and/or unanticipated departure from the procedures and/or processes approved by the sponsor and the IRB/IEC and agreed to by the investigator. Deviations usually have an impact on individual patients or a small group of patients and do not involve inclusion/exclusion or primary endpoint criteria.

The investigator or designee must document and explain in the patients' source documentation any deviation from the approved protocol. The investigator may implement a deviation from, or a change of, the protocol to eliminate an immediate hazard to study patients without prior IRB/IEC approval. As soon as possible after such an occurrence, the

implemented deviation or change, the reasons for it, and any proposed protocol amendment(s) should be submitted to the IRB/IEC for review and approval, to the sponsor for agreement, and to the regulatory authorities, if required.

10 Study Drug Materials and Management

All study medication will be dispensed by the pharmacy or an appropriately qualified member of the study staff assigned by the investigator to this task.

